12.1.4 Outcome of Adverse Events

The outcome of an adverse event will be classified into the following:

- (1) Recovered/resolved
The symptom or finding has disappeared or returned to the previous condition.
- (2) Recovering/resolving
The symptom or finding has almost disappeared or almost returned to the previous condition.
- (3) Not recovered/not resolved
When the symptom or finding has not improved and remains unchanged

(4) Recovered/resolved with sequelae

The symptom has resolved, but dysfunction that interferes with daily life is considered to have occurred due to the adverse event.

(5) Fatal

The patient died due to the adverse event.

12.1.5 Reporting of Adverse Events

Adverse events will be reported from the time of informed consent through the end of the follow-up examination. All adverse events will be documented in the source documents. The eCRF should include adverse events occurring in relation to this study from the time of informed consent to the start of investigational product administration and adverse events occurring after the start of investigational product administration. The evaluation in the observation period will be performed using the observations and tests at the registration in the observation period as a baseline, and the evaluation in the treatment period will be performed using the observations and tests at the registration in the treatment period as a baseline.

The principal investigator or subinvestigators will notify the sponsor of any adverse event or serious medical event including death which is reported or observed by a physician after the end of the follow-up examination and whose causal relationship with the investigational product cannot be ruled out.

12.1.6 Follow-up of Adverse Events

If an adverse event occurs, the principal investigator or subinvestigator will immediately take appropriate measures and follow up the event until it is confirmed to have resolved or to be resolving. However, if follow-up of the adverse event cannot be continued for any of the following reasons, the reason will be entered in the eCRF:

- The causal relationship with the investigational product cannot be evaluated because other treatment was performed.
- The follow-up becomes difficult due to transfer to another hospital, etc.
- The patient refuses to be followed.
- The patient dies.
- Although the adverse event has not resolved or is not resolving, the principal investigator or subinvestigator considers that the adverse event is stable or no further improvement is expected.

12.2 Serious Adverse Events

12.2.1 Definitions of Serious Adverse Events

An adverse event that results in one of the following at any dose is a serious adverse event:

- (a) Results in death;
- (b) Is life-threatening;

Note: The term “life-threatening” in the definition of “serious” refers to an event in which the patient was at risk of death at the time of the event; it does not refer to an event which hypothetically might have caused death if it were more severe.

- (c) Requires inpatient hospitalization or prolongation of existing hospitalization for treatment. The following are not considered hospitalizations for the purposes of assessing seriousness:
 - Emergency room visits < 24 hours;
 - Pre-planned hospitalization;
 - Hospitalization for study-related tests.
- (d) Results in persistent or significant disability/incapacity.
- (e) Is a congenital anomaly/birth defect (if exposure to a product just before conception or during pregnancy resulted in an adverse outcome in the child).
- (f) Other medically important conditions.

Note: Any other important medical event that based upon appropriate medical judgment may jeopardize the patient or may require medical or surgical intervention to prevent one of the other outcomes (a) to (e) listed in the definitions above. (eg, may not result in death, be life-threatening, or require hospitalization). Examples of such events include allergic bronchospasm requiring intensive treatment in an emergency room or at home, and blood dyscrasias, or convulsions that do not result in inpatient hospitalization, or development of drug dependency or drug abuse.

12.2.2 Reporting of Serious Adverse Events

A serious adverse event must be reported to the sponsor **within 24 hours** from the time the principal investigator or subinvestigator first becomes aware of the serious adverse event. Comprehensive information available at the time of initial reporting (including narrative description, medical history, and concomitant medications) needs to be provided with careful consideration regarding causality and serious criterion. The contact information for serious adverse events is shown below.

After the initial serious adverse event notification to the sponsor, all follow-up serious adverse event information will be submitted each time they become available (eg, diagnosis, outcome, causality assessment, results of specific investigations).

The principal investigator will submit further necessary information if it is requested by the sponsor, the head of the study site, or the IRB.

All serious adverse events occurring from the time of informed consent to the end of the follow-up examination will be reported to the sponsor. If any serious adverse event (including death) occurs outside the study period specified in the protocol, the principal investigator will report the serious adverse event to the sponsor only if he/she suspects it to be related to the investigational product.

Contact for serious adverse events

Clinical Development Department, Taiho Pharmaceutical Co., Ltd.

[name]

[REDACTED]
(8:40 am to 5:30 pm, except for Saturdays, Sundays, holidays, and December 29 to January 4)

For hours other than the above, contact the product leader or clinical team leader.

For the contact information for the product leader and the clinical team leader, see the attachment to the protocol.

12.2.3 Follow-up of Serious Adverse Events

Serious adverse events should be followed up in the same manner as the follow-up of adverse events. The follow-up procedure for adverse events is described in Section 12.1.6. If the follow-up of a serious adverse event cannot be continued, the reason will be recorded in the serious adverse event report form as well.

12.2.4 Expectedness to Investigational Product

The expectedness (known, unknown) to the investigational product will be determined based on the description of the Investigator's Brochure. If the nature and severity are consistent with the description, the event will be regarded as "known." Even if the event is listed in the Investigator's Brochure but if its nature and severity are not consistent with the description (eg, interstitial nephritis for acute renal failure, fulminant hepatitis for hepatitis), the event is regarded as "unknown."

Since no serious adverse event for which a causal relationship cannot be ruled out has occurred so far with TAC-302, all serious adverse events occurring in this study will be handled as "unknown."

12.3 Adverse Events of Special Interest

12.3.1 Definition of Adverse Events of Special Interest

Adverse events of special interest are not defined in this study.

12.4 Adverse Reactions

12.4.1 Definition of Adverse Reactions

Adverse events (including abnormal laboratory values) occurring during or after the treatment period for which a causal relationship with the investigational product is assessed as "reasonably possibility" by the principal investigator or subinvestigator are considered to be adverse reactions.

12.5 Other Information

12.5.1 Pregnancy

In this study, female patients of reproductive potential are required to practice contraception during the study period and for 30 days after the completion of investigational product administration. Male patients are required to practice contraception during the study period and for 90 days after the end of investigational product administration.

If obtaining pregnancy information such as pregnancy of a patient or the patient's partner during the specified contraception period, the principal investigator or subinvestigator will report the pregnancy information of the patient **within 24 hours** after he or she initially learned the pregnancy or the outcome of pregnancy. Pregnancy information will be recorded on a Pregnancy Form and reported to the sponsor by e-mail or fax. New and/or corrected information must be entered into the Pregnancy Form and submitted to the sponsor via email or fax.

The principal investigator or subinvestigator will follow the pregnancy of the patient and report the outcome. If the outcome of the pregnancy is a stillbirth, congenital anomaly/birth defect, or a serious event in the mother, it should be reported as a serious adverse event to the sponsor. Live births will be followed up by the principal investigator or subinvestigator, and any information that may be associated with the investigational product should be reported to the sponsor even after study completion.

12.5.2 Medication Errors

In this study, a medication error is defined as any unintentional error in prescribing, dispensing, or administering the drug used in the study while the drug is in the control of the healthcare professional or patient. The error may be related to the administration of a wrong drug, the nature of a drug, the route of administration, the dosage or frequency of administration specified in this protocol.

The following procedures should be followed:

- Any medication error with the investigational product should be reported to the sponsor immediately regardless of the occurrence of an adverse event (even if it does not fulfill the definition of a serious adverse event).
- There is no known antidote available for an investigational product overdose. Patients should be carefully monitored, and aggressive treatment should be performed with prophylactic and symptomatic therapies to prevent or treat possible adverse reactions.

13. STATISTICAL CONSIDERATIONS

Statistical analyses will be performed according to the following plan. Details will be specified in a separately prepared statistical analysis plan. The first version of the statistical analysis plan will be prepared before unblinding.

13.1 Analysis Plan

13.1.1 Timing of Statistical Analysis

Statistical analysis will be performed after completion of the study in all patients in this study. Before unblinding, preliminary investigation (blind review) of the distribution of efficacy and safety measurements or endpoints and the relationships between items will be performed, and details such as the handling of patient data and the method of statistical analysis will be finalized.

13.1.2 Analysis Sets and Criteria for Handling Patient Data

13.1.2.1 Analysis set

The definitions of the analysis sets in this study are as follows.

Table 13.1.2.1-1 Definition of Analysis Sets

Analysis set	Definition
Screening patients	The set of all patients who provided informed consent
All enrolled patients in the observation period	The set of all patients who were enrolled in the observation period
All enrolled patients in the treatment period	The set of all patients who were enrolled in the treatment period
All treated patients in the observation period	The set of patients enrolled in the observation period who took the investigational drug at least once
All treated patients in the treatment period	The set of patients enrolled in the treatment period who took the investigational drug at least once
Full analysis set(FAS)	The set of patients enrolled in the treatment period who took the investigational drug for the treatment period at least once and who had at least 1 efficacy endpoint measurement before the start of the treatment period and in the treatment period
Per protocol set(PPS)	The set of patients in the full analysis set (FAS), excluding patients who met any of the following criteria: (1) Being discovered to have a violation of the inclusion criteria (2) Being discovered to meet any of the exclusion criteria (criteria affecting efficacy evaluation) (3) A compliance rate for the treatment period of < 80%

	
(4) Being administered prohibited concomitant drugs or prohibited concomitant therapy considered likely to influence efficacy evaluation
 
(5) No evaluation of the primary endpoint at week 12 of the treatment period

--	---

If there are patients in unforeseen situations with respect to whether they belong to analysis sets, the sponsor will decide how to handle these patients after discussion with personnel including the medical expert, before unblinding.

13.1.2.2 Criteria for Handling Patient Data

The criteria for handling patient data in this study are as follows.

If there are patients with problems associated with the handling of patient data in this study other than those below, the sponsor will decide how to handle these patients after discussion with personnel including the medical expert, before unblinding.

- (1) Handling of missing values and abnormal values
 - The handling of missing values for efficacy endpoints will be designated separately for each analysis.
 - Missing values for safety endpoints will not be imputed, and when percentages such as the incidence of adverse events are calculated, in analysis of the observation period, the analysis set will be used as the denominator, and in analysis of the treatment period, the patients in the analysis set who take the investigational drug for the treatment period at least once will be used as the denominator.
 - All measured data will be used in analysis except for abnormal values for which there is an obvious reason, such as laboratory values affected by hemolysis at the time of blood collection. If any abnormal values are excluded from analysis, these values will be identified and the reasons for excluding them will be shown.
- (2) Handling of data from patients administered treatment for a group different from the group they are assigned to
 - In analysis of all treated patients and the PPS, data from patients administered treatment for a group different from the group they are assigned to will be handled as data for the group with the regimen actually administered.
 - For analyses using the FAS, data will be handled as data from the randomized assigned group.

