4.3 Discontinuation Criteria for Individual Patients

Administration of the investigational drug will be discontinued in a patient meeting any of the following criteria. Discontinuation criteria for individual patients are shown below:

- (1) It becomes unfeasible to continue administration due to the occurrence of an adverse event
- (2) The patient requests withdrawal of his/her consent
- (3) Major noncompliance with the study procedures is observed.
- (4) The patient becomes unable to continue the study due to circumstances such as moving house, being transferred to another medical institution or being too busy
- (5) It is discovered that the patient is not in the target population for this study (the patient does not meet the inclusion criteria, or meets any of the exclusion criteria).
- (6) The patient becomes pregnant.
- (7) Because the effect of the investigational drug is incomplete or symptoms have worsened, the principal investigator or subinvestigator determines that administration should be discontinued.
- (8) It becomes necessary to discontinue the patient from the study for any other reason in the opinion of the principal investigator or subinvestigator.

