- 7) Time window for the follow-up examination: This will be performed 1 to 2 weeks after the end of week 12 of the treatment period. If the patient discontinued during the treatment period, it will be performed 1 to 2 weeks after the final dose of the investigational drug.
- 8) At discontinuation: The designated observations and examination items will be performed as far as possible. For patients providing informed consent but not enrolled in the treatment period, the observations and tests relating to safety evaluation will be performed as far as possible.
- 9) If the designated observations or tests are performed in the period of 14 days before registration in the observation period, even if this is before informed consent is obtained, these can be used as data at registration in the observation period.
- 10) PFS will be performed on the same date as uroflowmetry and measurement of the post void residual by ultrasound as far as possible.
- 11) For evaluating BVE, measurement of the post void residual by ultrasound will be performed after uroflowmetry.
- 12) Concomitant drugs/concomitant therapy and evaluation of adverse events: These will be investigated from informed consent to the end of follow-up.

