13.1.3.3 Safety Analysis

The following analysis will be performed by group in the patients treated in the treatment period.

- (1) Adverse events

The following analyses will be performed:

 - The incidences of adverse events will be calculated.
 - For each adverse event item, the numbers of patients who experience adverse events and the incidences of adverse events will be displayed by severity.
 - Incidences will be calculated by time of onset of adverse events in the treatment period.
 - A list of the adverse event term, severity, date of onset, action taken, outcome of the adverse event, causal relationship with the investigational drug and comment

about the adverse events will be prepared for each adverse event item by patient, for all adverse events occurring from the start of administration of the investigational drug to the date of the end of the follow-up examination.

(2) Adverse reactions

- Adverse reactions will be analyzed in a similar manner to adverse events (except the preparation of lists).

(3) Blood pressure, pulse rate, and body temperature

- Summary statistics for blood pressure, pulse rate and body temperature at each evaluation time point will be calculated.
- For blood pressure and pulse rate, summary statistics for the change in the measured value at each evaluation time point relative to directly before the start of administration of the investigational drug for the treatment period will be calculated.

(4) 12-lead electrocardiography

The QT interval corrected with the Fridericia method (QTcF), which is an examination item in 12-lead electrocardiography, will be used.

- For the QTcF interval and heart rate, summary statistics for measured values will be calculated for each evaluation time point.
- For the QTcF interval and heart rate, summary statistics for the change in the measured value at each evaluation time point relative to directly before the start of administration of the investigational drug for the treatment period will be calculated.
- For the QTcF interval, the measured values at each evaluation time point were divided into categories and their frequencies will be tabulated.
- For the QTcF interval, the change in the measured value at each evaluation time point relative to directly before the start of administration of the investigational drug for the treatment period were divided into categories and their frequencies will be tabulated.

(5) Laboratory Values

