8.3 Safety Analysis

The following analyses will be performed for each treatment group in patients treated in the treatment period.

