8.3.1 Adverse Events and Adverse Reactions

The following analyses will be performed at each time point.

- The numbers of patients who experienced adverse events and the incidences of adverse events will be displayed. Similar analysis will be performed for adverse reactions. Similar analysis will also be performed by age (≥ 65 years and < 65 years). In addition, similar analysis will be performed by age (≥ 75 years and < 75 years).
- For each adverse event item, the numbers of patients who experienced adverse events and the incidences of adverse events will be displayed. Similar analysis will be performed for adverse reactions. Similar analysis will also be performed by age (≥ 65 years and < 65 years). In addition, similar analysis will be performed by age (≥ 75 years and < 75 years).
- For each adverse event item, the numbers of patients who experienced adverse events and the incidences of adverse events will be displayed by severity. Similar analysis will be performed for adverse reactions.
- The incidence of adverse events in the treatment period will be presented by time of onset (at or before Week 2 of the treatment period; after Week 2 of the treatment period and at or before Week 4 of the treatment period; after Week 4 of the treatment period and at or before Week 8 of the treatment period; after Week 8 of the treatment period and at or before Week 12 of the treatment period; after Week 12 of the treatment period; and follow-up observation). Similar analysis will be performed for adverse reactions.
- All adverse events that occurred from the start of study treatment to the end date of the follow-up observation will be listed by the adverse event variable of each patient, together with the adverse event term, severity, date of onset, action, outcome, causal relationship with the study drug, and comments.
- The incidence of serious adverse events will be calculated. Similar analysis will be performed for adverse reactions.
- The incidence of adverse events leading to discontinuation/dose interruption will be calculated. Similar analysis will be performed for adverse reactions.

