11.2 Handling of Dropouts or Missing Data

Handling of missing values in efficacy endpoints is specified for each analysis.

Missing data for safety endpoints will not be imputed.

Other than abnormal values for which there is an obvious rationale, such as the effect of hemolysis due to blood collection on laboratory test values, all measured data will be used for analysis. If abnormal values are excluded from the analysis, they will be specified and the reasons for exclusion will be stated.

In addition, in post-hoc exploratory analysis, for each analyzed item, the handling of missing values will be decided appropriately depending on the method of analysis and the characteristics of the endpoints being analyzed.

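### The adverse-event onset table keeps all patients treated in the treatment period as its denominator, so late-interval incidence understates risk among patients still observed

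*Protocol*

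**What the plan says.** Protocol 13.1.2.2(1) sets the base for safety percentages in general terms. It applies "when percentages such as the incidence of adverse events are calculated", and for the treatment period it states that "the patients in the analysis set who take the investigational drug for the treatment period at least once will be used as the denominator". It makes no exception for tables split by time.

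The protocol's Safety Analysis section (13.1.3.3) then plans that "Incidences will be calculated by time of onset of adverse events in the treatment period". SAP 8.3.1 repeats this, "The incidence of adverse events in the treatment period will be presented by time of onset", and names six categories: up to Week 2, Weeks 2 to 4, Weeks 4 to 8, Weeks 8 to 12, after Week 12, and follow-up. Neither section gives a number at risk, person-time or an exposure-adjusted rate. SAP 8.3 only names the population: "The following analyses will be performed for each treatment group in patients treated in the treatment period". SAP 11.2 adds: "Missing data for safety endpoints will not be imputed".

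On observation after early stopping, footnote 7 to protocol Table 5-2 says of the follow-up examination: "If the patient discontinued during the treatment period, it will be performed 1 to 2 weeks after the final dose of the investigational drug". Protocol 12.1.5 ends routine adverse-event reporting at that examination. After it, only events for which a causal link to the drug cannot be excluded are to be notified.

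**The concern.** An onset table is read to see whether events appear late, persist or fade over the 12 weeks. That reading assumes that the patients in each column's denominator could have had an event recorded in that interval.

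Take a patient who stops at Week 3. The follow-up examination falls at about Week 4 to 5, and routine collection then ends. This patient can add nothing routinely to the Weeks 8 to 12 column but is counted there as if observed without an event. The same holds for everyone who has left before an interval begins. A fall in incidence across the columns may then reflect attrition alone.

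Stopping need not be unrelated to tolerability. The first discontinuation criterion in protocol 4.3 is "It becomes unfeasible to continue administration due to the occurrence of an adverse event". If one arm loses more patients, its late columns are diluted more than those of the other arm.

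**Working it through.** The documents give no adverse-event rate and no dropout rate for this table, so there is no figure of the plan's own to reproduce. The sample-size rationale is blacked out, which is not held against the plan.

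**Inputs from the documents.** 75 patients (protocol synopsis; SAP 2.2.1) allocated 2:1 (protocol section 3): 75 × 2/3 = 50 on TAC-302 and 75 × 1/3 = 25 on placebo.

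**Assumed inputs.** The number of patients with an event in a late interval (*e*) and the number who left observation before it began (*d*).

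**Formulas.** For an arm of size *n*:

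- shown incidence = *e* / *n*
- incidence among those still observed = *e* / (*n* − *d*)
- so shown = still-observed incidence × *r*, with *r* = (*n* − *d*) / *n*
- shown ratio = still-observed ratio × *r*(TAC-302) / *r*(placebo)

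**1. One arm.** TAC-302, *n* = 50, *e* = 6:

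| Left before interval | Shown | Among those still observed |
|---|---|---|
| 0 | 6/50 = 12.0% | 6/50 = 12.0% |
| 5 (10%) | 6/50 = 12.0% | 6/45 = 13.3% |
| 10 (20%) | 6/50 = 12.0% | 6/40 = 15.0% |

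**2. Equal stopping in both arms.** Assume 20% vs 10% among those still observed, a difference of 10 points and a ratio of 2.0.

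- 10% stopped in each arm: 20% × 0.90 = 18.0% vs 10% × 0.90 = 9.0%. The difference is 9 points and the ratio 2.0.
- 20% stopped in each arm: 16.0% vs 8.0%. The difference is 8 points and the ratio 2.0.

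Only the absolute difference shrinks.

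**3. Unequal stopping, same 20% vs 10%.**

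- 10% (TAC-302) vs 0% (placebo) stopped: 18.0% vs 10.0%, ratio 1.80.
- 20% vs 4% stopped: 20% × 0.80 = 16.0% vs 10% × 0.96 = 9.6%, ratio 1.67.

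**4. In patients.** With 10 TAC-302 and 1 placebo patient gone, and 6 and 3 patients with events, the plan shows 6/50 = 12.0% vs 3/25 = 12.0%. Among those still observed it is 6/40 = 15.0% vs 3/24 = 12.5%, a ratio of 1.20. This equals 0.96 / 0.80, the ratio that this stopping pattern removes completely.

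**5. The other direction.** If placebo patients stop more (4% of TAC-302, 20% of placebo), the factor is 0.96 / 0.80 = 1.20 and the shown ratio is inflated by a fifth.

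**The case against.** The strongest reply is that the all-treated percentage is not an error. It is the share of treated patients whose event began in that interval, a well-defined quantity on the same base as overall incidence. The at-risk percentage answers a different question and is conditional on remaining under observation. If patients stop because of adverse events, the more susceptible leave, and the arms are less comparable in later intervals. This stands: neither figure is the true one, and the at-risk figure needs a caveat.

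The size argument also stands. Suppose 10 TAC-302 patients and no placebo patients leave. The gap among those still observed is then 15.0% − 12.0% = 3 points, when one placebo patient is 1/25 = 4 points. No between-arm test of adverse events is planned, so no stated conclusion turns on it. The plan also tabulates discontinuations with reasons and adverse events leading to discontinuation or interruption, summarises treatment duration, and lists each event with its onset date.

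SAP section 12 says the full set of analyses is in a separate report analysis plan. That plan is not available here, so it cannot be assumed to supply the missing numbers. The other tables limit how far a reader could be misled, but none shows how many patients were under observation in each interval.

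A reader might infer that the table will hide poorer tolerability of TAC-302. The documents do not support that. They give no dropout rate, and protocol 4.3 also allows stopping for incomplete effect or worsening symptoms, which could fall more heavily on placebo. Nor does the denominator include patients dosed only in the placebo observation period; the rule requires a treatment-period dose.

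**Conclusion.** The point holds in a limited form. As written, the denominator rule covers the onset table, and early stoppers stay in the base of intervals in which they are no longer routinely observed. Late-interval incidence is therefore too low as a measure of risk among patients still observed. The shortfall equals the fraction of the arm that has left: 12.0% shown against 13.3% at 10% dropout and 15.0% at 20%, for an assumed 6 patients with events among 50.

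At 10% dropout or less the effect is small. Distortion of the between-arm ratio requires unequal stopping, and its direction depends on which arm stops more. The overall incidence, where all treated patients are the usual base, is not in question. Follow-up is little affected, because early stoppers are also due a follow-up examination; dilution there is confined to those who miss it. Severity is low: this is a descriptive table, and the size rests on assumed dropout and event counts.

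**What to change.** In protocol 13.1.2.2(1) and SAP 8.3.1:

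- Keep all patients treated in the treatment period as the denominator for overall incidence.
- For the four onset intervals up to Week 12, print by arm the number still under adverse-event observation at the start of the interval and give the incidence on that number. The all-treated percentage can stand beside it.
- For the category after Week 12, report counts only or merge it with follow-up. The Week 12 visit window runs from −3 to +7 days, so who is at risk there depends on visit timing and may be only a few patients.
- For follow-up, use the patients who entered follow-up.
- State whether an early stopper's event between the last dose and the follow-up examination belongs to the calendar interval or to follow-up, so that numerator and denominator match. SAP 8.3.1 does not say.
- Add a footnote that the at-risk percentages are conditional on remaining under observation.

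The cost is a few sentences and a little more programming from dates already collected. Patients who leave partway through an interval still count in full there; a rate per person-time would deal with that but is optional in a table of this kind.
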